### **8.1.1.2 Consent and Collection of Specimens for Future Biomedical Research**

The investigator or medically qualified designee will explain the future biomedical research consent to the participant, answer all of his/her questions, and obtain written informed consent before performing any procedure related to the future biomedical research substudy. A copy of the informed consent will be given to the participant.

### **8.1.2 Inclusion/Exclusion Criteria**

All inclusion and exclusion criteria will be reviewed by the investigator who is a qualified physician to ensure that the participant qualifies for the study.

### **8.1.3 Participant Identification Card**

All participants will be given a participant identification card identifying them as participants in a research study. The card will contain study site contact information (including direct telephone numbers) to be used in the event of an emergency. The investigator or qualified designee will provide the participant with a participant identification card immediately after the participant provides written informed consent. At the time of intervention allocation/randomization, site personnel will add the treatment/randomization number to the participant identification card.

The participant identification card also contains contact information for the emergency unblinding call center so that a healthcare provider can obtain information about study intervention in emergency situations where the investigator is not available.

### **8.1.4 Medical History**

For participants who are discontinued from study intervention but continue to be monitored in the study, all visits and procedures, as outlined in Section 1.3 – SoA, and Section 8.10.3 – Discontinued Participants Continuing to be Monitored in the Study, should be completed.

### **8.1.5 Prior and Concomitant Medications Review**

#### **8.1.5.1 Prior Medications**

The investigator or qualified designee will review prior medication use, including any protocol-specified washout requirement, and record prior medication taken by the participant within 28 days before the first dose of study intervention.

### **8.1.5.2 Concomitant Medications**

The investigator or qualified designee will record medication, if any, taken by the participant during the study.

All medications related to reportable SAEs and ECIs should be recorded as defined in Section 8.4.

All new anticancer therapy initiated after the study start must be recorded in the eCRF. If a participant initiates another anticancer therapy other than the assigned study intervention(s), the study intervention(s) should be discontinued and the participant will move into the survival follow-up phase; if a participant initiates a new anticancer therapy within 30 days after the last dose of the study intervention, the 30-day Safety Follow-up visit should occur before the first dose of the new therapy.

### **8.1.6 Assignment of Screening Number**

All consented participants will be given a unique screening number that will be used to identify the participant for all procedures that occur prior to study intervention assignment. Each participant will be assigned only 1 screening number. Screening numbers must not be re-used for different participants.

Any participant who is screened multiple times will retain the original screening number assigned at the initial screening visit. Specific details on the screening/rescreening visit requirements are provided in Section 8.10.1.

### **8.1.7 Assignment of Treatment/Randomization Number**

All eligible participants will be allocated and will receive a treatment number. The treatment number identifies the participant for all procedures occurring after treatment allocation. Once a treatment number is assigned to a participant, it can never be re-assigned to another participant.

A single participant cannot be assigned more than 1 treatment number.

### **8.1.8 Study Intervention Administration**

#### **8.1.8.1 Oral medication: Selumetinib**

Selumetinib is an oral medication, and is supplied as hard-shell capsules in strength of 25 mg. Participants should be instructed to take selumetinib capsules BID, in the morning and in the evening at approximately the same times every day.

Participants will be given clear instructions on how and when to take their study intervention. Participants will self-administer selumetinib except when a clinic visit is scheduled. During on-site visits, administration of study medication will be witnessed by the investigator and/or trial staff. The administration, the dose, the time of administration, as well as any immediate reactions at the time of intake will be documented in the eCRF.

For non-visit days, selumetinib will be taken at home. The participant will note the number of capsules taken, the time of administration, as well as any reactions including the date/time. Participants will be instructed to notify study site personnel of missed doses.

Study site staff will conduct capsule counts at regular intervals during study treatment. After the capsule count is performed, the remaining capsules will not be returned to the participant but will be retained by the investigative site until reconciliation is completed by the study monitor.

When a participant attends a study visit, he/she will bring any unused capsules. All participants must return their bottle(s) of selumetinib at the appropriate scheduled visit, when a new bottle will be dispensed.

### **8.1.8.2 Infusion: Pembrolizumab**

Administration of study medication will be witnessed by the investigator and/or study staff. The total volume of study intervention infused will be compared to the total volume prepared to determine compliance with each dose administered.

Refer to Section 6 for dose and treatment details.

### **8.1.8.3 Timing of Dose Administration**

#### **8.1.8.3.1 Timing for Administration of Selumetinib (MK-5618)**

Participants should be instructed to take selumetinib capsules  $12 \pm 2$  hours apart with a large glass of water (approximately 250 mL) in the morning and in the evening at approximately the same time every day.

On clinical day on which PK samples are scheduled, dosing should be delayed until arrival at the clinic and until the pre-dose PK sample has been taken.

Selumetinib will be taken BID for the first 2 weeks of every 3-week treatment cycle. Selumetinib will be administered prior to the pembrolizumab infusion on days when study treatments are administered on the same day. The Pharmacy Manual contains specific instructions for selumetinib storage, administration, and administration sequence for combination administration.

Escalation/dosing schedule (eg, direction of dose escalation, BID on/off intermittent dosing schedule) may be adjusted based on totality of data (PK, PD and safety) emerging throughout the study. Any adjustment made to the dosing schedule will be initiated through an amendment to this protocol.

#### **8.1.8.3.2 Timing for Administration of Pembrolizumab (MK-3475)**

Pembrolizumab 200 mg will be administered as a 30-minute IV infusion Q3W. Sites should make every effort to target infusion timing to be as close to 30 minutes as possible. However, given the variability of infusion pumps from site to site, a window of -5 minutes and +10

minutes is permitted (ie, infusion time is 30 minutes: -5 min/+10 min). The Pharmacy Manual contains specific instructions for pembrolizumab preparation of the infusion fluid and administration.

Every effort should be made to begin the first dose of study treatment on the day of allocation, but if this is not achieved, trial therapy should be initiated no later than 3 days from the date of allocation. All subsequent cycles of study treatment may be administered up to 3 days before or 3 days after the scheduled Day 1 of each cycle due to administrative reasons per the Investigator's judgment.

All study interventions will begin on Day 1 of each cycle after all pre-dose study procedures and assessments have been completed as detailed on the SoA – Section 1.3. All study interventions will be administered on an outpatient basis.

The Pharmacy Manual contains specific instructions for pembrolizumab storage and administration.

### **8.1.9 Discontinuation and Withdrawal**

Participants who discontinue study intervention prior to completion of the treatment period should be encouraged to continue to be followed for all remaining study visits as outlined in the SoA and Section 8.10.3.

When a participant withdraws from participation in the study, all applicable activities scheduled for the study visit should be performed (at the time of withdrawal). Any AEs that are present at the time of withdrawal should be followed in accordance with the safety requirements outlined in Section 8.4.

#### **8.1.9.1 Withdrawal From Future Biomedical Research**

Participants may withdraw their consent for future biomedical research. Participants may withdraw consent at any time by contacting the principal investigator for the main study. If medical records for the main study are still available, the investigator will contact the Sponsor using the designated mailbox ([contact]). Subsequently, the participant's consent for future biomedical research will be withdrawn. A letter will be sent from the Sponsor to the investigator confirming the withdrawal. It is the responsibility of the investigator to inform the participant of completion of withdrawal. Any analyses in progress at the time of request for withdrawal or already performed prior to the request being received by the Sponsor will continue to be used as part of the overall research study data and results. No new analyses would be generated after the request is received.

In the event that the medical records for the main study are no longer available (eg, if the investigator is no longer required by regulatory authorities to retain the main study records) or the specimens have been completely anonymized, there will no longer be a link between the participant's personal information and their specimens. In this situation, the request for specimen withdrawal cannot be processed.

### **8.1.10 Participant Blinding/Unblinding**

This is an open-label study; there is no blinding for this study.

### **8.1.11 Domiciling**

Not applicable.

### **8.1.12 Calibration of Equipment**

The investigator or qualified designee has the responsibility to ensure that any device or instrument used for a clinical evaluation/test during a clinical study that provides information about inclusion/exclusion criteria and/or safety or efficacy parameters shall be suitably calibrated and/or maintained to ensure that the data obtained is reliable and/or reproducible. Documentation of equipment calibration must be retained as source documentation at the study site.

## **8.2 Efficacy Assessments**

### **8.2.1 Tumor Imaging and Assessment of Disease**

The process for image collection and transmission to the iCRO can be found in the Site Imaging Manual. Tumor imaging is strongly preferred to be acquired by computed tomography (CT). For the abdomen and pelvis, contrast-enhanced magnetic resonance imaging (MRI) may be used when CT with iodinated contrast is contraindicated, or when mandated by local practice. MRI is the strongly preferred modality for imaging the brain. The same imaging technique regarding modality, ideally the same scanner, and the use of contrast should be used in a participant throughout the study to optimize the reproducibility of the assessment of existing and new tumor burden and improve the accuracy of the assessment of response or progression based on imaging.

Note: for the purposes of assessing tumor imaging, the term “investigator” refers to the local investigator at the site and/or the radiological reviewer located at the site or at an offsite facility.

Imaging of chest, abdomen, and pelvis is typical. The Site Imaging Manual will include detailed instructions for specific tumor types and clinical scenarios.

Although RECIST 1.1 references to a maximum of 5 target lesions in total and 2 per organ, Merck allows a maximum of 10 target lesions in total and 5 per organ, if clinically relevant to enable a broader sampling of tumor burden.

#### **8.2.1.1 Initial Tumor Imaging**

Initial tumor imaging at Screening must be performed within 28 days prior to the date of Cycle 1 Day 1 (C1D1).

Tumor imaging performed as part of routine clinical management is acceptable for use as screening tumor imaging if they are of diagnostic quality and performed within 28 days prior to the date of C1D1.

Participants with previously treated brain metastases may participate provided they have stable brain metastases (ie, without evidence of progression by imaging confirmed by MRI if MRI was used at prior imaging, or confirmed by CT imaging if CT used at prior imaging) for at least 4 weeks prior to the first dose of study intervention. Any neurologic symptoms must have returned to baseline and participants must have no evidence of new or enlarging brain metastases, and have not used steroids for brain metastases for at least 28 days prior to study initiation as per local site assessment. This exception does not include carcinomatous meningitis, as participants with carcinomatous meningitis are excluded regardless of clinical stability.

If brain imaging is performed to document the stability of existing metastases, MRI should be used if possible. If MRI is medically contraindicated, CT with contrast is an acceptable alternative.

### **8.2.1.2 Tumor Imaging During the Study**

The first on-study imaging assessment should be performed at 9 weeks (63 days  $\pm$ 7 days) from the date of first dose of study drug intervention. Subsequent tumor imaging should be performed every 9 weeks (63 days  $\pm$ 7 days) or more frequently if clinically indicated. Imaging timing should follow calendar days and should not be adjusted for delays in cycle starts. Imaging should continue to be performed until disease progression is identified by the investigator, the start of new anticancer treatment, withdrawal of consent, or death, whichever occurs first.

Objective response should be confirmed by a repeat imaging assessment. Tumor imaging to confirm PR or CR should be performed at least 4 weeks after the first indication of a response is observed. Participants will then return to regular scheduled imaging every 9 weeks, starting with the next scheduled imaging time point. Participants who receive additional imaging confirmation do not need to undergo the next scheduled tumor imaging if it is less than 4 weeks later; tumor imaging may resume at the subsequent scheduled imaging time point.

Per iRECIST (Section 8.2.3), disease progression should be confirmed by the site 4 to 8 weeks site-assessed first radiologic evidence of PD in clinically stable participants. Participants who have unconfirmed disease progression may continue on treatment at the discretion of the investigator until progression is confirmed provided they have met the conditions detailed in Section 8.2.3. Participants who receive confirmatory imaging do not need to undergo the next scheduled tumor imaging if it is less than 4 weeks later; tumor imaging may resume at the subsequent scheduled imaging time point if clinically stable. Participants who have confirmed disease progression by iRECIST as assessed by the site will discontinue the treatment. Exception is detailed in Section 8.2.3.

### **8.2.1.3 End of Treatment and Follow-up Tumor Imaging**

For participants who discontinue study intervention, tumor imaging should be performed at the time of intervention discontinuation ( $\pm$ 4-week window). If previous imaging was obtained within 4 weeks prior to the date of discontinuation, then imaging at intervention discontinuation is not mandatory. For participants who discontinue study treatment due to documented disease progression, this is the final required tumor imaging the investigator elects not to implement iRECIST.

For participants who discontinue study treatment without documented disease progression, every effort should be made to continue monitoring disease status by tumor imaging using the same imaging schedule used while on treatment (see Section 8.2.1.2) until the start of a new anticancer treatment, disease progression, pregnancy, death, withdrawal of consent, or the end of the study, whichever occurs first.

### **8.2.2 RECIST 1.1 Assessment of Disease**

RECIST 1.1 will be used by the investigator as the primary measure for assessment of tumor response, date of disease progression, and as a basis for all protocol guidelines related to disease status (eg, discontinuation of study treatment). Although RECIST 1.1 references a maximum of 5 target lesions in total and 2 per organ, this protocol allows a maximum of 10 target lesions in total and 5 per organ, if clinically relevant to enable a broader sampling of tumor burden.

### **8.2.3 iRECIST Assessment of Disease**

iRECIST is based on RECIST 1.1 but adapted to account for the unique tumor response seen with immunotherapeutic drugs. iRECIST will be used by investigator/local radiology reviewers to assess tumor response and progression, and to make treatment decisions. This protocol allows a maximum of 10 target lesions in total and 5 per organ, if clinically relevant to enable a broader sampling of tumor burden. When clinically stable, participants should not be discontinued until progression is confirmed by the investigator, working with local radiology, according to the rules outlined below. This allowance to continue treatment despite initial radiologic PD takes into account the observation that some participants can have a transient tumor flare in the first few months after the start of immunotherapy, and then experience subsequent disease response. These data will be collected captured in the clinical database.

For participants who show evidence of radiological PD by RECIST 1.1 as determined by the investigator the investigator will decide whether to continue a participant on study treatment until repeat imaging is obtained (using iRECIST for participant management, see [Table 7](#)).

This decision by the investigator should be based on the participant's overall condition

Clinical stability is defined as the following:

- Absence of symptoms and signs indicating clinically significant progression of disease
- No decline in ECOG performance status
- No requirements for intensified management, including increased analgesia, radiation, or other palliative care

Any participant deemed clinically unstable should be discontinued from trial treatment at site-assessed first radiologic evidence of PD, and is not required to have repeat imaging for confirmation of PD by iRECIST.

If the investigator decides to continue treatment, the participant may continue to receive study treatment and the tumor assessment should be repeated 4 to 8 weeks later to confirm PD by iRECIST per investigator assessment. Images should continue to be sent in to the iCRO for potential retrospective blinded, independent central review.

If repeat imaging does not confirm PD per iRECIST, as assessed by the investigator, and the participant continues to be clinically stable, study treatment may continue and follow the regular imaging schedule. If PD is confirmed, participants will be discontinued from study treatment.

A summary of imaging and treatment requirements after first radiologic evidence of progression is provided in [Table 7](#).

Tumor flare may manifest as any factor causing radiographic progression per RECIST 1.1, including:

- Increase in the sum of diameters of target lesion(s) identified at baseline to  $\geq 20\%$  and  $\geq 5$  mm from nadir
  - Note: the iRECIST publication uses the terminology “sum of measurements”, but “sum of diameters” will be used in this protocol, consistent with the original RECIST 1.1 terminology.
- Unequivocal progression of non-target lesion(s) identified at baseline
- Development of new lesion(s)

iRECIST defines new response categories, including iUPD (unconfirmed progressive disease) and iCPD (confirmed progressive disease). For purposes of iRECIST assessment, the first visit showing progression according to RECIST 1.1 will be assigned a visit (overall) response of iUPD, regardless of which factors caused the progression.

At this visit, target and non-target lesions identified at baseline by RECIST 1.1 will be assessed as usual.

New lesions will be classified as measurable or non-measurable, using the same size thresholds and rules as for baseline lesion assessment in RECIST 1.1. From measurable new lesions, up to 5 lesions total (up to 2 per organ), may be selected as New Lesions – Target. The sum of diameters of these lesions will be calculated and kept distinct from the sum of diameters for target lesions at baseline. All other new lesions will be followed qualitatively as New Lesions – Non-target.

#### *Assessment at the Confirmatory Imaging*

On the confirmatory imaging, the subject will be classified as progression confirmed (with an overall response of iCPD), or as showing persistent unconfirmed progression (with an overall response of iUPD), or as showing disease stability or response (iSD/iPR/iCR).

#### *Confirmation of progression*

Progression is considered confirmed, and the overall response will be iCPD, if ANY of the following occurs:

- Any of the factors that were the basis for the initial iUPD show worsening:
  - For target lesions, worsening is a further increase in the sum of diameters of  $\geq 5\text{mm}$ , compared to any prior iUPD time point.
  - For non-target lesions, worsening is any significant growth in lesions overall, compared to a prior iUPD time point; this does not have to meet the “unequivocal” standard of RECIST 1.1
  - For new lesions, worsening is any of these:
    - An increase in the new lesion sum of diameters by  $\geq 5\text{mm}$  from a prior iUPD time point
    - Visible growth of new non-target lesions
    - The appearance of additional new lesions
    - Any new factor appears that would have triggered PD by RECIST 1.1.
- Any new factor appears that would have triggered PD by RECIST 1.1.

#### *Persistent iUPD*

Progression is considered not confirmed, and the overall response remains iUPD, if:

- None of the progression-confirming factors identified above occurs AND

- The target lesion sum of diameters (initial target lesions) remains above the initial PD threshold (by RECIST 1.1)

Additional imaging for confirmation should be scheduled 4 to 8 weeks from the imaging on which iUPD is seen. This may correspond to the next visit in the original visit schedule. The assessment of the subsequent confirmation scan proceeds in an identical manner, with possible outcomes of iCPD, iUPD, and iSD/iPR/iCR.

#### *Resolution of iUPD*

Progression is considered not confirmed, and the overall response becomes iSD/iPR/iCR if:

- None of the progression-confirming factors identified above occurs, AND
- The target lesion sum of diameters (initial target lesions) is not above the initial PD threshold.

The response is classified as iSD or iPR (depending on the sum of diameters of the target lesions), or iCR if all lesions resolve.

In this case, the initial iUPD is considered to be pseudo progression, and the level of suspicion for progression is “reset.” This means that the next visit that shows radiographic progression, whenever it occurs, is again classified as iUPD by iRECIST, and the confirmation process is repeated before a response of iCPD can be assigned.

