#### *Detection of progression at visits after pseudo progression resolves*

After resolution of pseudoprogression (ie, achievement of iSD/iPR/iCR), iUPD is indicated by any of the following events:

- Target lesions
  - Sum of diameters reaches the PD threshold (20% and 5 mm increase from nadir) either for the first time, or after resolution of previous pseudoprogression. The

nadir is always the smallest SOD seen during the entire trial, either before or after an instance of pseudoprogression.

- Non-target lesions
  - If non-target lesions have never shown unequivocal progression, their doing so for the first-time results in iUPD.
  - If non-target lesions had shown previous unequivocal progression, and this progression has not resolved, iUPD results from any significant further growth of non-target lesions, taken as a whole.
- New lesions
  - New lesions appear for the first time
  - Additional new lesions appear
  - Previously identified new target lesions show an increase of  $\geq 5$  mm in the new lesion sum of diameters, from the nadir value of that sum
  - Previously identified non-target lesions show any significant growth

If any of the events above occur, the overall response for that visit is iUPD, and the iUPD evaluation process (see Assessment at the Confirmatory Imaging above) is repeated. Progression must be confirmed before iCPD can occur.

The decision process is identical to the iUPD confirmation process for the initial PD, with one exception: if new lesions occurred at a prior instance of iUPD, and at the confirmatory imaging the burden of new lesions has increased from its smallest value (for new target lesions, the sum of diameters is  $\geq 5$  mm increased from its nadir), then iUPD cannot resolve to iSD or iPR. It will remain iUPD until either a decrease in the new lesion burden allows resolution to iSD or iPR, or until a confirmatory factor causes iCPD. Factors above indicate iUPD, the iUPD evaluation process repeats, just as on the first occurrence of iUPD. iUPD must be confirmed before iCPD can occur.

Additional details about iRECIST are provided in the iRECIST publication.

Table 7 Imaging and Treatment after First Radiologic Evidence of Progressive Disease

	Clinically Stable		Clinically Unstable	
	Imaging	Treatment	Imaging	Treatment

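### Once no worsening is seen, Section 8.2.3 keeps or resolves a first iUPD on the initial target-lesion sum alone, so an unchanged new lesion or unresolved non-target progression is coded iSD or iPR

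*Combined protocol and SAP*

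**What the plan says.** All of the rules below are in protocol Section 8.2.3.

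- **Trigger.** The first visit with RECIST 1.1 progression "will be assigned a visit (overall) response of iUPD, regardless of which factors caused the progression". The listed factors are the target sum (at least 20% and at least 5 mm from nadir), unequivocal non-target progression, and new lesions.
- **Confirmation of progression (iCPD).** This needs worsening of a factor behind the iUPD, or a new factor that would itself be PD. For target lesions the sum must rise by a further 5 mm or more, "compared to any prior iUPD time point". The non-target rule reads "For non-target lesions, worsening is any significant growth in lesions overall, compared to a prior iUPD time point". For new lesions the options are "An increase in the new lesion sum of diameters by" at least 5 mm, visible growth of new non-target lesions, or additional new lesions.
- **Persistent iUPD.** No confirming factor, and "The target lesion sum of diameters (initial target lesions) remains above the initial PD threshold (by RECIST 1.1".
- **Resolution of iUPD.** The first condition reads "None of the progression-confirming factors identified above occurs, AND"; the second, which must hold as well, reads "The target lesion sum of diameters (initial target lesions) is not above the initial PD threshold". When both hold, the grade is iSD or iPR according to the target sum, or iCR if all lesions have gone. The episode is called pseudoprogression and the suspicion of progression is reset.
- **Later episodes.** The process is the same with one exception. If new lesions occurred at an earlier iUPD and their burden has risen from its smallest value, the iUPD cannot resolve: "It will remain iUPD until either a decrease in the new lesion burden allows resolution to iSD or iPR", or until a confirming factor gives iCPD.

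Elsewhere, Section 8.2.2 makes RECIST 1.1 the primary measure of tumor response. Section 9.1 makes efficacy exploratory, and Section 9.6.1 leaves its methods to the sSAP. The table of contents lists a response rate by iRECIST under the efficacy endpoints (4.2.1.1.2); the text of that section is redacted.

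**The concern.** Three kinds of finding can open an iUPD, but once worsening is excluded only one of them, the target sum, can hold it open. For the other two, the persistent-iUPD category has no route at the first episode. A participant whose new lesion is still there, unchanged, leaves the iUPD state because of a measurement that had nothing to do with entering it.

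Two things are at stake. The label pseudoprogression is attached to progression that has not gone away. And a participant with shrunken target lesions plus a persisting new lesion can be graded iPR, so any iRECIST response rate built on these categories would lean upward.

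**Working it through.** The plan gives no figure to reproduce, so the check is a decision table plus small worked cases.

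**Step 1. Compare the two outcomes.** Persistent iUPD and resolution share the condition that no confirming factor occurs. They differ only in whether the initial target sum is above the initial PD threshold.

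**Step 2. Apply this to each cause at the first episode.** If the iUPD came only from a new or non-target lesion, the target sum had not reached the PD threshold. If it reaches the threshold at the repeat scan, that is a new PD factor and gives iCPD. So the combination needed for persistent iUPD cannot arise.

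| Sole cause of iUPD | That factor at repeat scan | Protocol result | If resolution were tied to the cause |
|---|---|---|---|
| Target sum | worse | iCPD | iCPD |
| Target sum | still above threshold, not worse | iUPD | iUPD |
| Target sum | resolved | iSD/iPR | iSD/iPR |
| Non-target | worse | iCPD | iCPD |
| Non-target | unresolved, not worse | **iSD/iPR** | **iUPD** |
| Non-target | resolved | iSD/iPR | iSD/iPR |
| New lesion | worse | iCPD | iCPD |
| New lesion | present, not worse | **iSD/iPR** | **iUPD** |
| New lesion | resolved | iSD/iPR | iSD/iPR |

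Exactly two rows change.

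**Step 3. Worked case (assumed values).** Baseline target sum 100 mm; nadir 60 mm; PD threshold = max(1.2 × 60, 60 + 5) = max(72, 65) = 72 mm. A 15 mm new lesion gives iUPD. At the repeat scan the target sum is 60 mm and the new lesion is still 15 mm. There is no confirming factor, and 60 is not above 72, so the iUPD resolves. Target change = (60 − 100)/100 = −40%. That is iPR if partial response means a fall of at least 30%, a cut-off the documents do not state. Had the new lesion reached 20 mm (15 + 5), the result would be iCPD.

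**Step 4. Exactly at the threshold (assumed values).** Nadir 50 mm; threshold = max(60, 55) = 60 mm. A sum of 60 mm is PD, because the trigger is at least 20% and at least 5 mm. An unchanged 60 mm at the repeat scan is not above 60, so it resolves to iSD. The later-episode text uses reaching the threshold, which agrees with the trigger and not with the resolution wording.

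**Step 5. Prior time points (assumed values).** Nadir 50 mm; first iUPD at 60; resolved at 55; second iUPD at 70; repeat 70. Within the second episode growth is 70 − 70 = 0 mm. Against the first, reset episode it is 70 − 60 = 10 mm, at least 5, so a literal reading of "compared to any prior iUPD time point" gives iCPD.

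**Step 6. Size per participant.** 1/50 = 2.0 percentage points at the planning sample size; 1/14 = 7.1 points at the maximum per dose level (Section 9.9).

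**The case against.** - **Resolution rests on the target sum alone.** A reader might infer this, but the text does not support it without qualification. Both conditions must hold, and the first removes every case with confirmed worsening. Nor does small growth always pass: the tolerance of under 5 mm applies to the measured new-lesion sum, while any visible growth of new non-target lesions confirms progression.
- **The later-episode rule contradicts the first-episode rule.** This is also tempting, but that exception applies only when new-lesion burden has increased from its smallest value; it does not address an unchanged lesion. The later-visit text even provides for earlier non-target progression that has not resolved. That may mean the authors accepted non-growing lesions as stable. The section refers to the iRECIST publication for further detail, which was not available, so no departure from it is claimed.
- **A reported response rate, or the choice of dose, is biased.** The documents do not show this. The endpoint text is redacted and the methods are in the sSAP. Section 8.2.1.2 also calls for responses to be confirmed at least 4 weeks later. The Synopsis and Section 4.1 let efficacy signals prompt other dose levels, but nothing ties iRECIST response to dose selection.
- **The new lesions could be added to the target sum to show growing disease.** Section 8.2.3 keeps those sums distinct, so no such total is used here.
- **The reset wording already limits comparison to the current episode.** This is a fair reading of the resolution and later-episode text together. It leaves the phrase in the confirmation rule in need of reconciling, not a proven error.

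What survives is the gap in Step 2, which the explicit rules decide without any outside source.

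**Conclusion.** The concern holds in limited form. At a first episode, when nothing has worsened and no new PD factor appears, the initial target sum alone separates persistent iUPD from resolution. Progression caused only by a new lesion or non-target growth that persists unchanged is then labelled pseudoprogression and graded iSD, or iPR if the target sum qualifies.

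The direction for the exploratory iRECIST response is upward. The overall size cannot be estimated: the documents give no frequency, so only the per-participant effect in Step 6 can be stated. The iPR grade rests on the assumed 30% cut-off, and entry into a reported rate depends on the unseen sSAP. RECIST 1.1 response, DLT evaluation and mTPI decisions do not depend on this rule. The at-threshold and prior-time-point issues are minor.

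**What to change.** **Analysis derivation only.** In the sSAP and the derivation code, assign iSD or iPR after an iUPD only when the factor or factors that caused it no longer meet the PD standard; otherwise keep iUPD. Treat a target sum exactly at the PD threshold as still meeting it, in line with the trigger and later-episode wording.

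**For the sponsor to reconcile.** The confirmation rule's reference to any prior iUPD time point should be reconciled with the reset described for resolution and later episodes. The confirmation, persistence, resolution and later-episode passages should also be reconciled with Table 7, because these categories steer treatment and scan timing. No clinical rule is proposed.

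**Cost.** A few sentences and some code. Some participants stay coded iUPD longer, possibly indefinitely with a stable new lesion, and the iRECIST response rate may be slightly lower. The derived category may differ from the one recorded at the site, so both should be kept.
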